9.1.2.1 Time point and general content

This interim analysis will commence when the last randomised subject in the phase IIa part of the trial has been followed up for safety and viral load data for 7 days after drug intake. The analysis will evaluate data regarding the safety and efficacy in subjects in the phase IIa part of the trial, and the main focus of this assessment will be the determination of additional relevant safety information, but also preliminary efficacy comparing subjects on DZIF-10c inhaled, DZIF-10c inhaled plus intravenous and Placebo with the focus on viral load changes to inform subsequent development stages.

Only a subset of data points are taken into consideration for this analysis.

9.1.2.2 Datapoints to be cleaned

Selected TLFs will be created and an overview of the specific TLFs will be available in a separate TOC document. The database should be as clean as possible before the snapshot is taken, and 7 days will be allocated to cleaning and reconciliation tasks after the last treated subject in the phase IIa part of the trial has been followed up for safety and viral load data for 7 days after drug intake. The data generated at the UKK will then be transitioned to BI via SAS transport files for analysis. Despite all reasonable cleaning efforts, it is conceivable that data points might still not be completely clean at the time point the data snapshot is performed as the trial is ongoing. Please note that all data are taken as they are, and no hard coding will be implemented.

The cleaning and reconciliation efforts will particularly focus on, but are not limited to, the following eCRF pages or data sources:

- Pages related to AEs
- Pages related to laboratory data
- Pages related to the administration of trial drug
- Pages related to subject disposition
- Pages related to baseline characteristics including concomitant medications
- Data sources related to nasopharyngeal or oropharyngeal viral load data (central testing)
- Data sources related to PK data (central testing)
- Data sources related to ADA data (central testing)

9.1.2.3 Analyses

The following entities will be evaluated at this interim analysis:

- Trial Subjects
 - Disposition of subjects
 - Demographic characteristics
 - Baseline Conditions
 - Concomitant Therapies
 - Exposure to study medication including compliance
- Safety
 - AE overall summary covering AEs with onset during the first 7 days after drug administration
 - Subjects with DLTs within 7 days of trial drug administration
 - Subjects with AEs within 7 days of trial drug administration
 - Subjects with drug-related AEs within 7 days of trial drug administration
 - Subjects with AEs leading to trial drug administration discontinuation
 - Subjects with SAEs within 7 days of trial drug administration
 - Subjects with AESIs within 7 days of trial drug administration
 - Subjects with transitions of CTCAE grades at baseline and worst grade within 7 days of trial drug administration
 - Subjects with clinically relevant lab abnormalities within 7 days of trial drug administration
- Preliminary Efficacy
 - Descriptive summary outputs of absolute viral load (based on nasopharyngeal swabs) in SARS-CoV-2-infected individuals, as well as absolute and relative changes from baseline, for each assessment time point.
 - Outputs for phase IIa part only:
 - Plots of absolute change from baseline in viral load by treatment arm
 - Time-weighted average change in viral load
 - Mixed effect Model for Repeated Measures (MMRM) of absolute change from baseline in viral load
- Preliminary PK/ADA (by trial part)
 - The same endpoints and assessments as listed in [Sections 5.2.2.1](#) and [5.2.2.2](#) will be performed, if data allows.

The safety outputs will be repeated covering the first 28 days after drug administration as well as the whole trial duration and from day 9 until day 91. Any table created will be accompanied by a corresponding listing.

In addition to these outputs based on the expansion part, a complete re-run of the analyses of the escalation part (and covered during interim analysis 1 already) will be performed.

Please note that all these outputs will also be included in the final CTR.

9.2 EXAMPLE CODE

The provided sample code will have to be modified to suit the needs of the corresponding analysis.

9.2.1 Change from baseline

9.2.1.1 Time-weighted average change in viral load

Change from Baseline in Viral load:

```
#####
%MACRO auc (idvar =, dsname =, timevar =, yvar =, resultds =);
  %LOCAL lastid;
  %* All data manipulations are to be made outside of the macro;
  %* Sort dataset -> 1st data point is the starting point;
  PROC SORT DATA = &dsname OUT = _tmp;
    BY &idvar &timevar;
  RUN;

  %* Get last idvar;
  DATA _null_;
    y = COMPBL ("&idvar");
    y1 = COMPRESS (y);
    n = LENGTH (y) - LENGTH (y1);
    CALL SYMPUT ('lastid', COMPRESS (PUT (n+1, 5.)));
  RUN;

  %PUT lastid = &lastid;
  %LET lastvar = %SCAN (&idvar, &lastid, %STR ( ));

  DATA _tmp1;
    SET _tmp;
    RETAIN _ltime _lyvar _difftime _mintime;
    BY &idvar;
```

```

IF FIRST.&lastvar THEN DO;
  _ltime = &timevar;
  _lyvar = &yvar;
  _difftime = .;
  _mintime = &timevar;
END;
IF NOT FIRST.&lastvar THEN DO;
  auccomp = 0.5 * (&yvar + _lyvar) * (&timevar - _ltime);
  diff = (&yvar - _lyvar);
  difft = (&timevar - _ltime);
  _ltime = &timevar;
  _lyvar = &yvar;
  IF last.&lastvar THEN _difftime = &timevar - _mintime;
  OUTPUT;
END;
RUN;

PROC SUMMARY DATA = _tmp1;
BY &idvar;
VAR auccomp;
OUTPUT OUT = &resultds._pre SUM = auc;
RUN;

DATA &resultds;
MERGE &resultds._pre _tmp1 (WHERE = (_difftime NE .) KEEP = &idvar
_difftime);
BY &idvar;
auc = auc / _difftime;
RUN;
%MEND;

%auc (idvar = subject swab_type gene, dsname = rawdata3, timevar = day, yvar = log_cp_ml_d,
resultds = auc_result);
#####

```

9.2.1.2 Mixed effect Model for Repeated Measures (MMRM) of absolute change from baseline in viral load

Change from Baseline in Viral load via MMRM approach:

```
#####

```

```

ods exclude all;
ods output Diff0=diff0 classlevels=cl ConvergenceStatus=cs;
proc mixed data=viral_small_sim cl order=internal covtest;
  class usubjid trt01pn ady;
  model chg = antibs base base*ady trt01pn*ady / solution ddfm=Kenwardroger
  outpred=outpred1;
  repeated ady / type=un subject=usubjid;
  lsmeans trt01pn*ady / pdiff=control ("100" "&cutoffdays") obsmargins cl alpha=0.05
  slice=ady;
run;
ods exclude none;
#####

```

Where:

- usubjid = subject
- trt01pn = treatment arm (here numeric)
- ady = analysis day
- antibs = antibody status
- base = baseline viral load
- chg = change from baseline in viral load
- cutoffdays = day for analysis → 7 (primary analysis) or 28 (sensitivity analysis)

Note that the reference level in the code above (“100”) has to be adapted to the level used in the study.

9.2.1.3 Mixed effect Model for Repeated Measures (MMRM) of viral load over time for mean viral load trajectories based on MMRM over time

Mean absolute viral load over time via MMRM approach:

```
#####

```

```

ods exclude all;
ods output Diff0=diff0 classlevels=cl ConvergenceStatus=cs;
proc mixed data=viral_small_sim cl order=internal covtest;
  class usubjid trt01pn ady;
  model vl = antibs trt01pn*ady / solution ddfm=Kenwardroger outpred=outpred1;
  repeated ady / type=un subject=usubjid;
  lsmeans trt01pn*ady / pdiff=control ("100" "&cutoffdays") obsmargins cl alpha=0.05
  slice=ady;
run;

```

```
ods exclude none;
```

```
#####

```

Where:

- usubjid = subject
- trt01pn = treatment arm (here numeric)
- ady = analysis day
- antib = antibody status
- vl = viral load at day for analysis
- cutoffdays = day for analysis → 7 (primary analysis) or 28 (sensitivity analysis)

Note that the reference level in the code above ("100") has to be adapted to the level used in the study.

9.2.2 Time-To-Event

9.2.2.1 Log-rank test

Time to resolution of self-assessed SARS-CoV-2-related symptoms:

```
#####

```

```
ods output Quartiles = quartiles_raw HOMTESTS = logrkp_raw;
title "Unstratified log rank test";
PROC LIFETEST data=tte_analysis_allpat METHOD = km plots = (s, lls) ;
  TIME ady * cnsr(1);
  STRATA trt01p / TEST = logrank;
  SURVIVAL CONFTYPE = linear;
RUN;
ods output close;
```

```
#####

```

Where:

- cnsr = censoring variable (1=censored)
- trt01p = treatment arm
- ady = analysis day

Note that this has to be implemented for each symptom separately.

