#### **5.9.4. Assignment of Trial Participants to Treatment Groups**

In the expansion cohort (**Group 2D**) participants are randomized 1:1:1 (placebo only:DZIF-10c inhalation and placebo i.v.:DZIF-10c inhalation and DZIF-10c i.v.) into the trial groups without stratification. Randomization will be implemented by a 24/7-Internet service (ALEA 17.1, FormsVision BV, Abcoude, NL) and prepared centrally by the Institute of Medical Statistics and Computational Biology (IMSB) at the University of Cologne.

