7.6.2.5 Time to resolution of self-assessed SARS-CoV-2-related symptoms

A log-rank test will be used to evaluate the effect of DZIF-10c on time to resolution of self-assessed SARS-CoV-2-related symptoms compared to Placebo over 29 days. A Cox proportional-hazards model will be used to derive the hazard ratio and 95 % CI between each of the two randomised treatment regimens that were assigned DZIF-10c and the placebo regimen (Hazard ratios <1 will favour DZIF-10c). This will be done for each symptom (cough, feverishness, body ache, headache, sore throat, shortness of breath, loss of taste or smell) separately as well as together for all symptoms. Breslow's method for handling ties will be used. Kaplan-Meier plots by treatment group will also be presented and the rates at day 29 compared.

This endpoint will be evaluated on subjects from the subject set TS.

7.6.2.6 Differences of viral spike gene sequences obtained before and after study drug administration and the investigation of the effect of observed mutations on viral sensitivity to DZIF-10c in neutralization assays

These analyses will be performed by UKK and reported in a separate report which will be appended to the CTR.

7.6.2.7 The activity and frequency of SARS-CoV-2-reactive immune cells following DZIF-10c administration

As described in Section 4, these analyses will be performed by UKK and will not be included in the CTR but might be reported elsewhere.

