9.2.2.2 Cox proportional-hazards model

Time to resolution of self-assessed SARS-CoV-2-related symptoms:

```
#####
ods output ParameterEstimates = param_est_raw GlobalTests = global_test_raw;
title "Unstratified cox model";
PROC PHREG DATA= tte_analysis_allpat ;
  CLASS trt01p (REF = "Placebo") ;
  MODEL ady * cnsr(1) = trt01p /TIES = BRESLOW;
  HAZARDRATIO trt01p /CL = WALD ALPHA = 0.05;
  ODS OUTPUT HAZARDRATIOS = hazard_raw;
RUN;
ods output close;
#####
```

Where:

- cnsr = censoring variable (1=censored)
- trt01p = treatment arm
- ady = analysis day

Note that the reference level in the code above (“Placebo”) has to be adapted to the level used in the study, and that the evaluation has to be implemented for each symptom separately.

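### The log-rank code tests whether any of the three Group 2D arms differ, so its p-value answers neither regimen-versus-placebo question set in SAP 7.6.2.5 (minor)

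*SAP*

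**What the plan says.** In Group 2D, "participants are randomized 1:1:1" to placebo by both routes, inhaled DZIF-10c with intravenous placebo, or inhaled plus intravenous DZIF-10c (Protocol 5.9.4). The planned size is 20 per arm (Protocol 8.2).

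For symptom resolution, SAP 7.6.2.5 states: "A log-rank test will be used to evaluate the effect of DZIF-10c on time to resolution of self-assessed SARS-CoV-2-related symptoms compared to Placebo". It does not say whether this means each regimen, the two regimens pooled, or all three arms at once. The next sentence is specific for the Cox model, which is to give the "hazard ratio and 95 % CI between each of the two randomised treatment regimens that were assigned DZIF-10c and the placebo regimen". Kaplan-Meier plots by treatment group are also planned.

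The log-rank code in SAP 9.2.2.1 reads "PROC LIFETEST data=tte_analysis_allpat METHOD = km plots = (s, lls" and groups with "STRATA trt01p / TEST = logrank", where "trt01p = treatment arm". The p-value is taken from "HOMTESTS = logrkp_raw". The only adaptation noted under this code is to repeat it for each symptom. The Cox code in SAP 9.2.2.2 reads the same dataset and sets placebo as the reference level.

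**The concern.** The question asked in 7.6.2.5 is a comparison with placebo, and there are two regimens to compare. The code returns one p-value for the null hypothesis that all three curves are equal. A small value says that some arm differs from some other. It does not say which arm, or whether placebo is involved. It is not the test that belongs with either of the two hazard ratios planned in the same paragraph.

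This matters because the trial separates inhalation from inhalation plus infusion throughout, including in its primary objectives. A p-value introduced as the effect of DZIF-10c compared with placebo should say something about at least one of those regimens against placebo. The p-value from this code does not, and it may sit beside two hazard ratios whose intervals point elsewhere.

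**Working it through.** **1. What the code tests.** Three levels of the grouping variable give 3 − 1 = 2 degrees of freedom. The 5% critical value is 5.99, against 3.84 for a 1-df comparison of two arms.

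**2. Are all three arms in the dataset?** The SAP does not define `tte_analysis_allpat`. The Cox code reads the same dataset and has to produce a hazard ratio for each DZIF-10c regimen against placebo, which needs all three arms. The log-rank call has no WHERE clause. Three arms is therefore the natural reading, though an inferred one.

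**3. Is there a planned figure to reproduce?** No. The SAP and protocol give no alpha, power, event count or effect size for this test. The figures below are illustrations.

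**4. Simulation.**
- From the documents: three equal arms of 20, whole-day diary times, censoring at day 29.
- Assumed: exponential resolution times, placebo median 10 days, the hazard ratios shown (above 1 means faster resolution), all 20 per arm symptomatic, two-sided 0.05.
- 3000 trials per scenario. The Monte Carlo standard error is at most √(0.5 × 0.5 / 3000) = 0.9 percentage points.

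| True HR vs placebo: inhaled / combined | Global 2-df p<0.05 | Inhaled vs placebo p<0.05 | Combined vs placebo p<0.05 | Global significant, inhaled vs placebo not |
|---|---|---|---|---|
| 1 / 1 | 6% | 5% | 5% | 3% |
| 1 / 2 | 57% | 5% | 54% | 52% |
| 1 / 2.5 | 82% | 5% | 77% | 77% |
| 2 / 2 | 57% | 55% | 55% | 10% |
| 1 / 0.5 | 48% | 5% | 47% | 43% |
| 0.7 / 1.5 | 50% | 18% | 23% | 34% |

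In the last scenario, about 15% of all trials have a significant global test while neither regimen differs significantly from placebo. There the contrast between the two DZIF-10c arms contributes to the result.

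**5. Fewer informative participants.** SAP 5.3.5 censors anyone without the symptom at baseline at day 1, so fewer than 20 per arm will usually inform a given symptom. With 10 per arm, inhaled-only null and combined HR 2, the global test is significant in 32–34% of trials and inhaled versus placebo in 6–7% (placebo median 7 or 10 days).

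**6. Analytic cross-check, assuming every participant has an event.**
- Pairwise, HR 2, 40 events (Schoenfeld): ln 2 × √(40/4) = 2.19; power = Φ(2.19 − 1.96) = 59%.
- Global, one arm at HR 2, 60 events: noncentrality = 60 × (1/3 × 2/3) × (ln 2)² = 6.41; power with 2 df = 61%.

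Both agree with the simulation once censoring is allowed for. Pairwise tests therefore give up little power for the active arm: 54% against 57% at HR 2, and 77% against 82% at HR 2.5.

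**The case against.** The case for leaving the plan alone has four parts.

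**The code is only an example.** SAP 9.2 says the sample code will have to be modified to suit each analysis, and other blocks are plainly templates: the code for proportions has no treatment variable at all. This is a fair point, but it does not settle the matter. The text of 7.6.2.5 leaves the comparison open, so the code is the only place that resolves it. The note under the code asks only for repetition by symptom, and a programmer who follows it delivers the 2-df test. The MMRM code (`pdiff=control`) and the Cox code (placebo reference) do specify comparison with a control.

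**The per-arm results are shown anyway.** This stands. A reader might infer that the plan would credit an effect in one arm to both regimens. No section says so. The Cox hazard ratios, their intervals and the Kaplan-Meier curves would show which arm differs.

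**The simulated percentages are not error rates.** This also stands. A reader might take 57% or 82% as a false-positive rate. In those scenarios one arm truly differs, so rejecting equality of all three curves is correct; under complete equality the test rejects in about 6%. The figures show only that a significant result carries no information on which regimen differs from placebo.

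**No decision depends on it.** This stands too. Symptom resolution is an exploratory endpoint, the protocol plans only to describe it, it is not on the list for interim analysis 2, and the SAP limits the display of p-values. A global test with per-arm Cox estimates is also a legitimate pairing, provided that it is named as such.

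**Conclusion.** The mismatch is real but minor. Run as printed on the three Group 2D arms, the code in 9.2.2.1 yields one 2-df p-value that can be attributed to neither regimen against placebo and corresponds to neither Cox hazard ratio. Under the assumed rates, an effect in the combined arm alone makes it significant in about 57% (HR 2) to 82% (HR 2.5) of trials while inhaled versus placebo stays near 5%. When the two DZIF-10c arms diverge in opposite directions (HR 0.7 and 1.5), it is significant in about 15% of trials with neither regimen differing significantly from placebo.

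These sizes depend on the assumed median, hazard ratios and number of symptomatic participants. The degrees of freedom depend on the dataset holding all three arms, which the Cox code implies. The documents do not support the stronger conclusion that the trial would report an effect for a regimen that has none.

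**What to change.** - In SAP 7.6.2.5, state that two nominal 1-df log-rank tests are reported per symptom, and likewise for the all-symptom analysis: inhaled versus placebo, and inhaled plus intravenous versus placebo. Report each with its own hazard ratio.
- In SAP 9.2.2.1, run the test on each DZIF-10c arm plus placebo. Alternatively, add `DIFF=CONTROL('Placebo')`, save the pairwise-comparison table as well, and report its unadjusted p-values. Adding that option alone is not enough, because the current output line would still store only the global test in `logrkp_raw`.
- If a three-arm p-value is kept, label it as a global 2-df test of any difference.

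The cost is a sentence in the SAP and a few lines of code, with no new data. The downside is two nominal p-values per symptom instead of one: with seven symptoms and one analysis of all symptoms together, 8 × 2 = 16 instead of 8. SAP 7.5 already treats p-values for the secondary endpoints as nominal and unadjusted; the same sentence could be repeated for this endpoint.

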9.2.2.2 Cox proportional-hazards model

Time to resolution of self-assessed SARS-CoV-2-related symptoms:

```
#####
ods output ParameterEstimates = param_est_raw GlobalTests = global_test_raw;
title "Unstratified cox model";
PROC PHREG DATA= tte_analysis_allpat ;
  CLASS trt01p (REF = "Placebo") ;
  MODEL ady * cnsr(1) = trt01p /TIES = BRESLOW;
  HAZARDRATIO trt01p /CL = WALD ALPHA = 0.05;
  ODS OUTPUT HAZARDRATIOS = hazard_raw;
RUN;
ods output close;
#####
```

Where:

- cnsr = censoring variable (1=censored)
- trt01p = treatment arm
- ady = analysis day

Note that the reference level in the code above (“Placebo”) has to be adapted to the level used in the study, and that the evaluation has to be implemented for each symptom separately.

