### **5.2.7. Assessment of Time to Symptom Resolution**

Participants will be asked to self-record selected SARS-CoV-2 symptoms (cough, feverishness, body ache, headache, sore throat, shortness of breath, changes in/loss of taste of taste and smell) from the day of study drug administration through the day 28 visit and grade them as absent, mild, moderate, or severe using a participant diary (**Groups 2A-2D**).

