### **8.2. Sample Size Considerations**

During the dose escalation phase of the trial, a routine 3+3 trial design will be employed.

Since this is a hypothesis-generating trial, no formal sample size calculation is done for the randomized expansion study part. Selection of the group size included considerations of feasibility for an early phase first-in-human trial in quarantined individuals while facilitating outcome measures that can inform later stage trials. 60 participants will be included in the

expansion cohort with 20 participants per arm. Assuming a similar rate of participants experiencing Adverse Events as observed in a previous clinical trial of a SARS-CoV-2-neutralizing antibody in ambulatory SARS-CoV-2-infected participants, the following confidence intervals for the rate of Adverse Events in the expansion cohort can be calculated per group of 20 participants:

Rate of AEs (Participants)	90% confidence interval (Participants with AEs)
20%	[5% ; 35%]
25%	[9% ; 41%]
30%	[13% ; 47%]

While this exploratory trial is not powered to determine statistically significant differences in the change of the viral load between the treatment arms in the expansion cohort, simulations based on effects observed for previously reported SARS-CoV-2 neutralizing antibody responses indicate that an AUC ratio  $>1.45$  between a treatment arm of with a similar effects and controls can be observed with  $>80\%$  probability at a group size of 20.

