5.3.5 Time to resolution of self-assessed SARS-CoV-2-related symptoms

Date of symptom assessment for an individual subject and symptom will be obtained from the subject diary for every symptom (namely: cough, feverishness, body ache, headache, sore throat, shortness of breath, change in/loss of taste and smell) separately. Symptom evaluation scoring will take place every day on a 4-point scale (0=absent; 1=mild; 2=moderate; 3=severe), and the results entered in a subject diary. Date of resolution on the 4-point scale will be defined as the first day after drug intake where a SARS-CoV-2-related symptom is recorded as “0”. Any subsequent reoccurrence will not be considered.

For subjects with known date of symptom resolution within the first 28 days after drug intake the derivation will be as follows:

- Time to resolution [days] = Date of resolution of symptom – date of drug intake + 1

Subjects who did not experience any resolution of their existing symptom by day 29, or who have missing evaluation data, or who did not show a particular symptom at baseline will be censored according to the mechanism for censoring as described in [Table 5.3.5: 1](#) below. In particular, all subjects with no symptom at baseline will be censored at day 1, even if they later develop a symptom (after drug intake).

Table 5.3.5: 1 Censoring and Event Rules for Time to resolution of self-assessed SARS-CoV-2-related symptoms within the first 28 days after drug intake.

Rule #	Situation	Outcome (event or censored)	Date of event or censoring
1	Subject had a symptom at baseline and a resolution within the first 28 days and date of resolution is known	Event	Date of event
2	Subject had a symptom at baseline and a resolution within the first 28 days and date of resolution is unknown	Event	Imputed date of event
3	Subject had a symptom at baseline but no resolution within the first 28 days	Censored	Day 29 (28 days after first drug intake)
4	Subject had a symptom at baseline but resolution status within the first 28 days is unknown or a subject has missing assessment data	Censored	Date of last recorded consecutive follow-up entry of symptom status within the first 28 days after drug intake
5	Subject did not show a particular symptom at baseline	Censored	Day 1 (Date of drug intake)

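### The Cox model for symptom resolution leaves out the baseline score of the same symptom; if severity is prognostic, this costs power and leaves the hazard ratio open to chance imbalance

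*SAP*

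**What the plan says.** SAP 7.6.2.5 states: "A Cox proportional-hazards model will be used to derive the hazard ratio and 95 % CI between each of the two randomised treatment regimens" and placebo. It names no covariate or stratum. The code in SAP 9.2.2.2 agrees: "MODEL ady * cnsr(1) = trt01p /TIES = BRESLOW", under a title that calls the model unstratified. The log-rank test in 9.2.2.1 is also unstratified.

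The outcome and its natural baseline share one scale. SAP 5.3.5: "Symptom evaluation scoring will take place every day on a 4-point scale (0=absent; 1=mild; 2=moderate; 3=severe"). Protocol 5.2.7 has participants record the symptoms "from the day of study drug administration through the day 28 visit and grade them as absent, mild, moderate, or severe". The event is "the first day after drug intake where a SARS-CoV-2-related symptom is recorded as" zero. SAP 5.3.5 adds that "all subjects with no symptom at baseline will be censored at day 1, even if they later develop a symptom".

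On design, Protocol 8.2 plans an "expansion cohort with 20 participants per arm". In Protocol 5.9.4 "participants are randomized 1:1:1", without stratification.

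Elsewhere the SAP does adjust. In 7.5.2.2.3 the viral-load ANCOVA includes baseline viral load and antibody status. The MMRM includes those plus baseline-by-visit. No reason is given for treating symptoms differently.

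**The concern.** A participant who starts at 3 has further to go to reach 0 than one who starts at 1, so the baseline score is a natural candidate predictor of time to resolution. It takes the value 1, 2 or 3 in everyone who can have an event. Neither the analysis nor the randomisation accounts for it, and the arms are small.

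Two things are at stake if severity is prognostic. First, hazard ratios are non-collapsible: omitting a prognostic covariate gives a hazard ratio nearer 1 than the conditional one even when the arms are balanced, and the test loses power. Second, a chance difference in baseline severity between arms moves the estimate directly. Symptom resolution is the only clinical outcome with a planned model; hospitalisation and medical contacts are summarised descriptively (SAP 7.6.2.4).

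**Working it through.** **No figure to reproduce.** The documents give no power, event count, hazard ratio or severity effect for this endpoint. Everything below the design inputs is an assumption, shown as a range.

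**Inputs from the documents.** Three arms of 20 (Protocol 8.2); unstratified 1:1:1 allocation (Protocol 5.9.4); daily scores, censoring at day 29 (SAP 5.3.5); Breslow ties and a 95% Wald interval (SAP 9.2.2.2). Time is date of resolution minus date of intake plus 1, and resolution must fall after the day of intake, so the earliest event is day 2. Participants censored at day 1 are never in a risk set. Informative numbers per symptom are therefore at most 20 per arm.

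**Direction.** Here a hazard ratio above 1 means faster resolution on DZIF-10c, as follows from resolution being the event and placebo the reference. The remark in SAP 7.6.2.5 that ratios below 1 favour DZIF-10c does not fit this and needs separate correction.

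**Benchmark without a covariate.** Schoenfeld power for two equal arms is Φ(√(D/4)·ln HR − 1.96). At HR 2 (ln 2 = 0.693):

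- D = 40 events: Φ(2.192 − 1.96) = 59%
- D = 30: Φ(1.898 − 1.96) = 47%
- D = 20: Φ(1.550 − 1.96) = 34%

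The comparison is weak before any covariate is considered.

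**Simulation.** Three-arm Cox model; exponential times rounded up to days; placebo median 7 days at score 2; scores 1, 2 and 3 equally likely; conditional treatment HR 2.0; Wald test at 1.96; 4,000 replicates per row; 20 symptomatic per arm. HR is the median estimate and SE is the mean standard error of the log hazard ratio.

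| Severity HR per grade | Treatment only: HR / SE / power | With baseline score: HR / SE / power | Gain (points) |
|---|---|---|---|
| 1.0 (none) | 1.93 / 0.340 / 49.3% | 1.94 / 0.346 / 49.3% | 0.0 |
| 0.8 | 1.91 / 0.339 / 48.4% | 1.96 / 0.346 / 50.4% | 2.0 |
| 0.7 | 1.86 / 0.339 / 44.8% | 1.93 / 0.346 / 48.5% | 3.7 |
| 0.5 | 1.73 / 0.338 / 35.4% | 1.91 / 0.347 / 46.4% | 11.0 |
| 0.35 | 1.59 / 0.341 / 25.9% | 1.88 / 0.352 / 43.7% | 17.8 |

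**Where the gain comes from.** Approximate power is Φ(ln HR / SE − 1.96). In the 0.5 row:

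- treatment only: Φ(0.545/0.338 − 1.96) = Φ(−0.35) = 36%
- adjusted: Φ(0.648/0.347 − 1.96) = Φ(−0.09) = 46%
- only the SE changed: Φ(0.545/0.347 − 1.96) = Φ(−0.39) = 35%

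The estimate moves away from 1; the standard error works slightly the other way.

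**Robustness.**

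- Scores in 40/40/20% and a median of 8 days at score 2, with severity HR 0.74, 0.61, 0.50 and 0.37 per grade: power 47.5→49.2%, 42.0→47.6%, 34.0→43.9% and 27.0→42.8%.
- A further run at the same four severity effects: 49→51%, 40→45%, 35→45% and 29→47%, with about one point lost when severity had no effect.
- 14 symptomatic per arm, severity HR 0.7, 0.5 and 0.35: 32→35%, 26→34% and 20→31%.
- 8 per arm, same severity effects: 19→21%, 16→20% and 13→19%.
- No treatment effect: the median HR is about 1 and rejection about 4-6% for both models.

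**Chance imbalance.** With scores 1, 2 and 3 equally likely the variance is 2/3, so the SD of the difference in mean score between two arms of 20 is √(2 × (2/3)/20) = 0.26 grade. To first order, a one-SD imbalance at severity HR 0.5 multiplies the unadjusted hazard ratio or its inverse by up to exp(0.258 × 0.693) = 1.20. This is an upper guide, because the treatment-only fit attenuates this shift too.

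**The case against.** The strongest reply is that the plan is coherent as it stands. A treatment-only hazard ratio, an unstratified log-rank test and Kaplan-Meier curves all describe the marginal comparison. The endpoint is exploratory, p-values are nominal and their display is limited (SAP 4.3 and 7.5), no sample size was calculated, and symptom resolution is not among the efficacy outputs of interim analysis 2. Protocol 8.1.4 allows covariate models, and SAP 9.2 calls the code a sample to be modified.

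Much of this stands, and it rules out three stronger readings that a reader might infer:

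- **That the planned hazard ratio is biased.** It validly estimates a marginal effect; the severity-conditional ratio is a different quantity. Neither is biased under no effect. Part of the shortfall from 2.0 comes from daily rounding with Breslow ties, since 1.93 appears even when severity has no effect.
- **That the planned estimate is less precise.** The standard error of the log hazard ratio is slightly smaller without the covariate, about 0.34 against 0.35.
- **That power is certainly lost.** This needs baseline severity to predict resolution time, which the documents do not establish. The simulations also fit the same linear severity effect that generated the data, which favours adjustment.

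The latitude argument is weaker. Permission is not commitment: the SAP text agrees with the code, and the adaptations noted in 9.2.2.2 are the reference level and repetition by symptom. Without prespecification, adjusting after an imbalance is seen would be a post hoc choice.

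**Conclusion.** The point holds in a conditional and modest form. The omission and the availability of the diary score are plain in the text. The size rests on an assumed conditional hazard ratio of 2, 20 symptomatic participants per arm and a severity effect that the documents do not give. On that basis the power loss is about 2 points if the effect is weak, roughly 5 to 10 if moderate and up to about 18 if strong. If there is no severity effect, adjustment gains nothing and may cost about one point. For less common symptoms both the power and the gain are smaller. What adjustment buys is power against the conditional effect and protection from chance imbalance. No stated power or decision rule is undermined, so this is a worthwhile improvement to an exploratory analysis, not a correction of an error.

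**What to change.** In SAP 7.6.2.5 and 9.2.2.2:

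- Add the baseline diary score of the symptom analysed as a numeric covariate: `MODEL ady*cnsr(1) = trt01p base_sev`.
- Define that score as the day-of-dosing entry under the baseline rule of SAP 6.7. This needs stating, because Protocol 5.2.7 does not say that the first entry is pre-dose and SAP 5.4.1.5 lists baseline symptoms only as present or absent.
- For the all-symptom analysis, prespecify one summary, the baseline total score.
- Report the hazard ratio as conditional on baseline severity.
- Keep the unadjusted hazard ratio, log-rank test and Kaplan-Meier curves alongside.

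The cost is one model term using data already collected, one degree of freedom, a slightly larger standard error of the log hazard ratio, and a conditional rather than marginal interpretation.
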